## 8 ASSESSMENT OF STUDY VARIABLES

The data will be analyzed by Prometheus or an official designee (e.g., a contract research organization [CRO]).

### 8.1 Randomization

Subjects will be randomized in a 1:1 ratio based on two stratification factors: CDx status (+/-) and prior biologic experience (yes/no) in Cohort 1. If the study is expanded in Cohort 2, only CDx+ subjects will be randomized in a 1:1 ratio based on prior biologic experience (yes/no). Eligible subjects will be assigned a subject randomization number at baseline by the IRT system upon confirmation of study eligibility. Subjects who are re-randomized in OLE will retain their original subject numbers.

### 8.2 Justification of Sample Size

The study is planned to randomize up to approximately 170 subjects, approximately 120 in Cohort 1 and up to 50 in Cohort 2. A sample size of 60 per arm in Cohort 1 will enable a statistical power of > 80% for the primary endpoint at 1-sided significance level of 0.025 using Cochran-Mantel-Haenszel (CMH), assuming clinical remission rate of 5% for placebo and 24% for PRA023. Additionally, the sample size will confer > 80% power to achieve statistical significance for the 1st secondary endpoint of endoscopic improvement with an overall 1-sided alpha level of 0.025, assuming the endoscopic improvement rates are 15% and 38% for placebo and PRA023 groups, respectively.

Additionally, for analyses of the CDx+ population (combining CDx+ subjects from Cohort 1 and Cohort 2), a sample size of 40 per arm will provide a statistical power of  $\geq 80\%$  at a 1-sided alpha level of 0.025, according to a group sequential design with a non-binding futility interim analysis when approximately 18 subjects are anticipated per arm reach Week 12, assuming clinical remission rate of 5% for placebo and 31% for PRA023.

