--	--

	
For subjects assigned to the 100 mg Q4W OLE arm, the dose may be escalated to 250 mg Q4W if disease activity is not adequately controlled in the Investigator's opinion.
 
The study is being amended by the Sponsor to extend the OLE period beyond 132/134 weeks to Week 168/170 based on emerging safety data in both this study as well as a concurrent open-label Phase 2 study in Crohn's disease. This extension is to obtain safety data for at least 2 years' of PRA023 drug exposure for at least 100 subjects in this study, assuming 20% annual dropout rate. The OLE period may be further extended beyond 168/170 weeks based on emerging safety data in a future amendment.
 
The study also includes an optional PK sub-study during the IP for subjects who consent to additional PK sampling.

SAMPLE SIZE:	
The study is planned to randomize up to approximately 170 subjects, approximately 120 in Cohort 1 and up to 50 in Cohort 2. A sample size of 60 per arm in Cohort 1 will enable a statistical power of > 80% for the primary endpoint at 1-sided significance level of 0.025 using Cochran-Mantel-Haenszel (CMH), assuming clinical remission rate of 5% for placebo and 24% for PRA023. Additionally, the sample size will confer > 80% power to achieve statistical significance for the 1st secondary endpoint of endoscopic improvement with an overall 1-sided alpha level of 0.025, assuming the endoscopic improvement rates are 15% and 38% for placebo and PRA023 groups, respectively.
 
Additionally, for analyses of the CDx population (combining CDx+ subjects from Cohort 1 and Cohort 2), a sample size of 40 per arm will provide a statistical power of <math>\geq 80\%</math> at a 1-sided alpha level of 0.025, according to a group sequential design with a non-binding futility interim analysis when approximately 18 subjects per arm are anticipated to reach Week 12, assuming clinical remission rate of 5% for placebo and 31% for PRA023.

SUBJECT TYPE:	Male or female subjects $\geq 18$ years of age with moderately to severely active UC.
FORMULATIONS:	PRA023 will be supplied in 10 mL vials each containing 500 mg PRA023 (60 mg/mL concentrate for solution for infusion) for IV administration after reconstitution.

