
Statistical Methods:
	
Statistical methods will be detailed in the Statistical Analysis Plan. The SAP will provide details about the method of analysis and specific planned analyses, and will be prepared and approved by Prometheus Biosciences and its designees before study database lock and unblinding of subject treatment assignments.
 
The analysis populations are defined as follows:
 
 
• Full analysis set (FAS) from Cohort 1: all subjects randomized and treated in Cohort 1
 
• FAS for CDx+: all CDx+ subjects who are randomized and treated in both Cohort 1 and Cohort 2
 
• Safety analysis set: all subjects treated
 
 
The following analyses will be performed:
 
Efficacy:
 
The efficacy assessment will test for the difference between PRA023 and placebo groups in FAS.
 
The primary endpoint will be analyzed and compared between PRA023 and placebo treatment groups in FAS from Cohort 1. The primary endpoint, the proportion of subjects achieving clinical remission, will be tested between the 2 treatment groups at 1-sided significance level of 0.025 using CMH with stratification factors at randomization. If significant, the 1st secondary endpoint of proportion of subjects achieving endoscopic improvement will be tested between the 2 treatment groups at 1-sided significance level of 0.025. If significant, the 2nd, 3rd, 4th, and 5th secondary endpoints will be tested sequentially, each at 1-sided significance level of 0.025. Testing for statistical significance will stop when the first endpoint is not statistically significant at level of 0.025 and all remaining p values will be nominal.
 
Treatment difference for primary and secondary endpoints for Cohort 1 will be estimated along with 95% CI for all subjects in FAS. The secondary

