## **6.4 Efficacy Assessment Description**

The 3-component Modified Mayo Score (stool frequency, rectal bleeding, and endoscopy) will be used to evaluate disease activity for primary and secondary endpoints. The Modified Mayo scoring system is a composite index consisting of 3 disease variables (each scored on a scale of 0 to 3, with higher scores indicating greater frequency or severity): stool frequency, rectal bleeding, and findings on endoscopy. The 3-component Modified Mayo Score range from 0 to 9 points and utilize 3 disease variables, with higher scores indicating more severe disease. The 4th component of the Modified Mayo Score, physician's global assessment (PGA, scored on a scale of 0 to 3, with higher score indicating greater severity of disease), will be collected and the fully Modified Mayo Score will be used as an exploratory assessment only. The Partial Mayo score

ranges from 0 to 9 points and utilizes the Mayo scoring system of stool frequency, rectal bleeding, and PGA without the endoscopy subscore. See [Appendix 16.1](#) for a description of Modified Mayo Scoring Assessment.

For the current study, the following definitions will apply:

- The 3-component Modified Mayo Score Clinical Response (Clinical Response) – a reduction from Baseline  $\geq 2$  points and  $\geq 30\%$  in Modified Mayo Score, accompanied by a reduction  $\geq 1$  in rectal bleeding subscore or absolute rectal bleeding subscore  $\leq 1$ .
- The 3-component Modified Mayo Score Clinical Remission (Clinical Remission) – endoscopic subscore of 0 or 1, rectal bleeding subscore of 0, and stool frequency subscore of 0 or 1 and not greater than Baseline.
- Symptomatic remission – rectal bleeding subscore = 0 and stool frequency subscore = 0.
- Endoscopic improvement – Endoscopy subscore  $\leq 1$  with no friability.
- Histologic Remission – Geboes score  $\leq 3.1$ .
- Histologic-endoscopic mucosal improvement – Geboes score  $\leq 3.1$  and endoscopy subscore  $\leq 1$  with no friability.
- Mucosal Healing – Geboes score  $\leq 2B.1$  and endoscopy subscore of  $\leq 1$ .

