### 9.3.2 Evaluation of Efficacy Parameters

The efficacy assessment will test for the difference between PRA023 and placebo groups in FAS.

The primary endpoint will be analyzed and compared between PRA023 and placebo treatment groups in FAS from Cohort 1. The primary endpoint, the proportion of subjects achieving clinical remission, will be tested between the 2 treatment groups at 1-sided significance level of 0.025 using CMH with stratification factors at randomization. If significant, the 1st secondary endpoint of proportion of subjects achieving endoscopic improvement will be tested between the 2 treatment groups at 1-sided significance level of 0.025. If significant, the 2nd, 3rd, 4th, and 5th secondary endpoints will be tested sequentially, each at 1-sided significance level of 0.025. Testing for statistical significance will stop when the first endpoint is not statistically significant at level of 0.025 and all remaining p values will be nominal.

Treatment difference for primary and secondary endpoints for Cohort 1 will be estimated along with 95% CI for all subjects in FAS. The secondary endpoints in CDx+ subjects will be summarized and compared between PRA023 and placebo groups in FAS for CDx+, while the treatment difference will be estimated with 95% CI. Additional efficacy analysis will be detailed in SAP.

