#### Physician's global assessment§

- 0 = Normal
  - 1 = Mild disease
  - 2 = Moderate disease
  - 3 = Severe disease
- Subscore, 0 to 3

† Each subject serves as his or her own control to establish the degree of abnormality of the stool frequency.

‡ The daily bleeding score represents the most severe bleeding of the day.

§ The physician's global assessment acknowledges the three other criteria, the subject's daily recollection of abdominal discomfort and general sense of wellbeing, and other observations, such as physical findings and the subject's performance status.

\* Modified Mayo score considers mild disease (endoscopy score of 1) to be without any friability.

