2 MODIFICATION TO APPROACH FOR MULTIPLICITY

The following text will replace the content of Section 6.10 of the SAP V01.

A closed hierarchical procedure will be used to control for multiple comparisons of primary and key secondary endpoints. The order of testing will be primary endpoint, followed by the key secondary endpoints in the order as displayed in [Table 1](#). If at any point in this sequential procedure the null hypothesis is not rejected, the testing procedure will be terminated. All subsequent analyses would be considered exploratory.

The primary endpoint will be analyzed and compared between PRA023 and placebo treatment groups in FAS from Cohort 1. The primary endpoint, the proportion of subjects achieving clinical remission, will be tested between the 2 treatment groups at 1-sided significance level of 0.025 using CMH. If significant, the secondary endpoints will be tested sequentially between the 2 treatment groups at significance level indicated in the table.

Table 1 Primary and Key Secondary Endpoints in Cohort 1

Endpoints	Analysis Population (1-sided alpha)
Primary	
Proportion of subjects in 3-component Modified Mayo Score clinical remission (as defined by endoscopic subscore of 0 or 1, rectal bleeding subscore of 0, and stool frequency subscore of 0 or 1 and not greater than Baseline) at Week 12	FAS (0.025)
Secondary	

 • Proportion of subjects with endoscopic improvement (as defined by endoscopy subscore ≤ 1 with no friability) at Week 12 	FAS (0.025)

 • Proportion of subjects in 3-component Modified Mayo Score clinical response (as defined by a reduction from Baseline ≥ 2 points and $\geq 30\%$ in 3-component Modified Mayo Score, accompanied by a reduction ≥ 1 in rectal bleeding subscore or absolute rectal bleeding subscore ≤ 1) at Week 12 	FAS (0.025)

	<h2>Statistical Analysis Plan - Addendum</h2>
---	---

Version: 01

Status: Final

Endpoints	Analysis Population (1-sided alpha)

 Proportion of subjects with symptomatic remission (as defined by stool frequency (SF) subscore = 0 and rectal bleeding (RB) subscore = 0) at Week 12 	FAS (0.025)

 Proportion of subjects with histologic-endoscopic mucosal healing (defined as Geboes score \leq 2B.1 and endoscopy subscore \leq 1 with no friability) at Week 12 	Histology Analysis Set (0.025)

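### The >80% power stated for endoscopic improvement is single-test power (about 83%); through the required primary gate the protocol's own rates give about 77%.

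*Protocol*

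**What the plan says.** Section 8.2 plans 60 subjects per arm in Cohort 1. For the primary endpoint it claims more than 80% power at one-sided 0.025 by Cochran-Mantel-Haenszel (CMH), assuming clinical remission in 5% on placebo and 24% on PRA023. It then says that "the sample size will confer > 80% power to achieve statistical significance for the" first secondary endpoint, at an overall one-sided alpha of 0.025, "assuming the endoscopic improvement rates are 15% and 38% for placebo and PRA023 groups, respectively". The sample-size text in the synopsis makes the same claim. Neither place mentions the testing sequence in connection with this power.

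The sequence is set out elsewhere. Section 9.3.2 tests the primary endpoint "using CMH with stratification factors at randomization" and goes on to endoscopic improvement only if that test is significant: "Testing for statistical significance will stop when the first endpoint is not statistically significant at level of 0.025". The synopsis has the same rule, and both places give the consequence for the endpoints further down the sequence: "and all remaining p values will be nominal". SAP addendum section 2 keeps endoscopic improvement first after the primary and keeps the gate: "If at any point in this sequential procedure the null hypothesis is not rejected, the testing procedure will be terminated".

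**The concern.** Under this plan the endoscopic-improvement test cannot yield a formally significant result by itself. If the primary fails, its p value is nominal however small it is. So the event that section 8.2 describes, achieving statistical significance for the first secondary endpoint, requires two successes. A power figure for the second test alone overstates the chance of that event.

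At stake is how section 8.2 is read. A reader takes the chance of a formal endoscopic-improvement result to be above 80%. If the gated figure is below 80%, the claim fails for the procedure by which significance is actually declared.

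**Working it through.** **Inputs, all from the documents.** 60 per arm, 1:1, one-sided 0.025 (critical value 1.96). Remission 5% vs 24%; endoscopic improvement 15% vs 38% (section 8.2).

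**Step 1: reproduce the stated figure.** Normal approximation with pooled null variance: power = Φ[(d − 1.96·SE0)/SE1].

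- Endoscopic improvement: d = 0.23. SE0 = √(2 × 0.265 × 0.735/60) = 0.0806. SE1 = √((0.15 × 0.85 + 0.38 × 0.62)/60) = 0.0778. Power = Φ(0.926) = 0.823.
- Remission: d = 0.19. SE0 = √(2 × 0.145 × 0.855/60) = 0.0643. SE1 = √((0.05 × 0.95 + 0.24 × 0.76)/60) = 0.0619. Power = Φ(1.034) = 0.849.

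Both exceed 80%, so the protocol's figures reproduce as single-test power.

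**Step 2: how the endpoints overlap.** Remission requires "endoscopic subscore of 0 or 1, rectal bleeding subscore of 0, and stool frequency subscore of 0 or 1 and not greater than Baseline" (section 6.4). Endoscopic improvement is a subscore of at most 1 with no friability. The footnote to Appendix 16.1 says the "Modified Mayo score considers mild disease (endoscopy score of 1) to be without any friability". So a subject in remission always has endoscopic improvement, and each arm has three categories:

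| Arm | Remission (and improvement) | Improvement only | Neither |
|---|---|---|---|
| Placebo | 5% | 15 − 5 = 10% | 85% |
| PRA023 | 24% | 38 − 24 = 14% | 62% |

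No outside correlation is needed.

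**Step 3: power through the gate.** Gated power = P(remission test significant and endoscopic test significant), summed exactly over all outcomes of the two trinomials with 60 per arm.

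| Test statistic | Primary | Endoscopic alone | Both |
|---|---|---|---|
| Mantel-Haenszel, unstratified | 0.873 | 0.826 | **0.769** |
| Pooled z | 0.873 | 0.835 | 0.776 |
| Unpooled z | 0.892 | 0.837 | 0.790 |
| Mantel-Haenszel, continuity-corrected | 0.811 | 0.771 | 0.692 |
| Stratified CMH, four strata (simulated) | 0.873–0.875 | 0.829–0.830 | 0.771–0.773 |

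The stratified simulation comes closest to the planned analysis. It has no continuity correction and assumes the same rates in every stratum, a CDx+ share of about 30% to 40%, and a prior-biologic share of 50% to 70% (the range in the inclusion criteria).

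**Step 4: size and sensitivity.** 0.80 − 0.769 = 0.031 below the stated threshold; 0.826 − 0.769 = 0.057 below the single test. Moving both PRA023 rates by one point gives a gated power of 0.728 (23% and 37%) or 0.806 (25% and 39%), by the unstratified Mantel-Haenszel test.

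**The case against.** The best defence is that the sentence is correct as ordinary per-endpoint power. It gives one endpoint, its own two rates and an alpha, and never claims joint power. Overall alpha describes type I error and does not make the power a joint probability. The chance of success once the gate is open is 0.769/0.873 = 88%, also above 80%. The gate is fully disclosed in section 9.3.2. The gap is smaller than the uncertainty in the rates: 25% and 39% on PRA023 give 0.806. The replacement figures also depend on a continuity correction that the documents neither adopt nor rule out; SAP V01, which the addendum amends, is not among them.

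Much of this stands. Nothing is miscalculated for the single test, the gap is small, and 77% depends on the test statistic. But neither the single-test nor the conditional figure is the probability of achieving significance under this plan, and that is what section 8.2 says it gives. Disclosing the gate elsewhere does not tell the reader that the power ignores it. Uncertainty about the rates does not rescue a statement made conditional on stated rates. A continuity correction makes matters worse: it puts even the single test at 77%.

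**Conclusion.** The point holds, as a minor one. At the protocol's own rates and 60 per arm, the power to declare endoscopic improvement significant under the planned sequence is about 77%, not above 80%. The versions of the test range from 0.692 to 0.790. The stated figure is right only for the single test, at about 83%.

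The conclusion rests on the same endoscopy reading serving both endpoints, so that remission is nested in improvement, and on no allowance for dropout, since section 8.2 states none for Cohort 1. Nesting helps the plan: if the endpoints were independent, the uncorrected Mantel-Haenszel figure would be 0.873 × 0.826 = 0.721. The primary endpoint's power claim is unaffected. Estimates of the treatment difference with 95% confidence intervals are reported whatever the primary shows, and the endoscopic p value is then nominal, so what is overstated is only the chance of a formal claim.

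**What to change.** In section 8.2 and in the synopsis, restate the power for endoscopic improvement as about 83% for the single test and about 77% under the hierarchical testing procedure. Those figures are for CMH without continuity correction. If the planned test uses one, the corresponding figures are about 77% and 69%, so the sponsor should confirm the statistic when inserting them. Nothing else in the sample-size text needs to change.

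The cost is one clause in each place and a slightly less favourable stated figure. No subjects are added, and no test or analysis is altered.

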### 8.3 Evaluation of Safety Variables

Data will be summarized with respect to safety observations. Monitoring of AEs, physical examinations, vital signs, ECGs, safety and tolerability monitoring evaluations, clinical laboratory evaluations, and special procedures are detailed in [Section 6.3](#).

All available safety data for all randomized subjects who receive at least one dose of PRA023 will be included in the safety analysis, which will be primarily descriptive.

The safety variables will be:

- Hematology, chemistry, coagulation, and urinalysis
- Vital signs
- ECG parameters

- Physical examination
- AEs and SAEs
  - AEs of special interest: infections, acute infusion reaction (within 1 hour of completion of infusion), and peri-infusion reaction (within 24 hours of completion of infusion)
  - AEs in subjects who are ADA positive

## 9 STATISTICAL METHODOLOGY

This section describes the statistical analysis as it is foreseen at the time of planning the trial. Statistical methods will be further detailed in the SAP. The SAP will provide details about methods of analysis and the specific planned analyses, and will be prepared and approved by Prometheus Biosciences and its designees before study database lock.

Any deviations from the analysis plan, and the reasons for such deviations, and all alternative or additional statistical analyses that may be performed will be justified in the clinical study report.

All individual data as well as results of statistical analyses will be presented in individual subject data listings and statistical summary tables. In general, continuous variables will be summarized using the following standard descriptive summary statistics: number of observations, arithmetic mean, standard deviation (SD), coefficient of variation (CV), minimum, median and maximum. The geometric mean (GM) will be reported for PK and PD variables where appropriate. Categorical data will be summarized as number and percentage of subjects. Shift tables will be provided, where appropriate.

### 9.1 Analysis Populations

#### 9.1.1 Safety Analysis Set (SAS) Population

All subjects who received at least one dose of the study drug will be included in the safety evaluations.

#### 9.1.2 Full Analysis Set (FAS) Populations

The FAS population for Cohort 1: will be a subset of the Safety population and will include all subjects who have been randomized and treated in Cohort 1.

The FAS population for CDx+: will be all CDx+ subjects who are randomized and treated in both Cohort 1 and Cohort 2.

### 9.2 Interim Analysis

An interim analysis will be carried out when approximately 80% of subjects (approximately 96 subjects) in Cohort 1 have reached Week 12 or early terminated from the study. The DMC will review the unblinded efficacy and safety data and recommend on the continuation of enrollment into Cohort 2. Decision rules to continue Cohort 2 enrollment are to be determined according to the futility bounds of group sequential design of a sample size of 40 per arm with one interim analysis at the information fraction of 45%. Because the exact bounds will be calculated using the actual number of subjects with CDx+ included in the interim analysis, the final decision rules, along with sensitivity analysis, will be specified in the DMC SAP, prior to the interim analysis.

## 9.3 Statistical Analysis

### 9.3.1 Demographics and Baseline Characteristics

Demographic data (height, weight, age, sex, race, ethnic origin), and baseline characteristics including CDx status will be listed by subject and summarized by treatment group and for the overall FAS population.

### 9.3.2 Evaluation of Efficacy Parameters

The efficacy assessment will test for the difference between PRA023 and placebo groups in FAS.

The primary endpoint will be analyzed and compared between PRA023 and placebo treatment groups in FAS from Cohort 1. The primary endpoint, the proportion of subjects achieving clinical remission, will be tested between the 2 treatment groups at 1-sided significance level of 0.025 using CMH with stratification factors at randomization. If significant, the 1st secondary endpoint of proportion of subjects achieving endoscopic improvement will be tested between the 2 treatment groups at 1-sided significance level of 0.025. If significant, the 2nd, 3rd, 4th, and 5th secondary endpoints will be tested sequentially, each at 1-sided significance level of 0.025. Testing for statistical significance will stop when the first endpoint is not statistically significant at level of 0.025 and all remaining p values will be nominal.

Treatment difference for primary and secondary endpoints for Cohort 1 will be estimated along with 95% CI for all subjects in FAS. The secondary endpoints in CDx+ subjects will be summarized and compared between PRA023 and placebo groups in FAS for CDx+, while the treatment difference will be estimated with 95% CI. Additional efficacy analysis will be detailed in SAP.

